Primary clinical outcome: SAND hyporeactivity subscale (Siper et al., 2017). Secondary and exploratory outcomes targeting ASD symptom domains: ABC-SW (Aman et al., 1985) and other measures employed in Aim 1 (Table 1) based on results from Aim 1. Clinical outcomes will be measured by an independent evaluator who is blind to side effects to prevent the risk of bias, and, within subjects, the same evaluator will complete assessments across all visits. Electrophysiological markers and clinical measures will be collected at baseline, weeks 4, 8, and 12 of each phase. Safety and tolerability will be measured after two weeks in each phase and then

every four weeks thereafter during monitoring visits and phone calls using an adapted semi-structured interview, the Safety and Monitoring Uniform Report Form (SMURF); extensive clinical

Table 1: Clinical Outcome Measures		
Domain	Instrument	Measurement modality
Social	Aberrant Behavior Checklist - Social Withdrawal Subscale	Caregiver report
Language /Communication	MacArthur-Bates Communication Development Inventory Vineland Adaptive Behavior subscales Mullen Scales for Early Learning subscales	Caregiver report Caregiver report Direct assessment
Repetitive Behavior	Repetitive Behavior Scales-Revised Aberrant Behavior Checklist - Motor Stereotypies Subscale Sensory Profile Sensory Assessment for Neurodevelopmental Disorders	Caregiver report Caregiver report Caregiver report Direct assessment
Adaptive Behavior	Vineland Adaptive Behavior Scales-3	Caregiver report

and laboratory

assessments will occur every four weeks during visits (see Protection of Human Subjects).

Language testing will include standardized measures reliant on caregiver report and objective standardized assessments. Specifically, caregivers will report on a child's expressive and receptive verbal and non-verbal communication repertoire on the MacArthur-Bates Communication Development Inventory (MCDI; Fenton et al., 2007), which is a valid assessment of young children's language (Charman et al., 2003; Luyster et al., 2007). Although not normed in children above 30 months of age, preliminary data collected on this measure suggest that raw scores on the MCDI are useful in capturing the range of language functioning in our minimally verbal and intellectually disabled sample. The MSEL and Vineland will provide standardized assessments of receptive and expressive language, by direct assessment and parent interview, respectively.

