After the initial AE/SAE report, the investigator will actively follow each subject and provide further information on the subject's condition. All AEs and SAEs documented at a previous visit/contact and designated as not recovered/not resolved or recovering/resolving will be reviewed at subsequent visits/contacts. Investigators will follow-up subjects with SAEs or subjects withdrawn from the study as a result of an AE, until the event has resolved, subsided, stabilized, disappeared, the event is otherwise explained, or the subject is lost to follow-up. In the case of other non-serious AEs, until they complete the study or they are lost to follow-up. Clinically significant laboratory abnormalities will be followed until they have returned to normal, or a satisfactory explanation has been provided. The investigator may perform or arrange for the conduct of supplemental measurements and/or evaluations to elucidate as fully as possible the nature and/or causality of the AE or SAE.

Regulatory Reporting Requirements for Serious Adverse Events:

All safety data will be reported to Safety Monitoring Board and IRB every six months, or, in the case of any major safety concern or question, immediately. If any study stopping condition occurs, this will be reported immediately, and the study will be halted, pending review by these agencies. The investigator has a legal responsibility to promptly notify, as appropriate, both the local regulatory authority and other regulatory agencies about the safety of a product under clinical investigation. Prompt notification of SAEs by the investigator to the Study Contact for Reporting SAEs is essential so that legal obligations and ethical responsibilities towards safety of other subjects are met. The investigator, or responsible person according to local requirements, will comply with the applicable local regulatory requirements related to the reporting of SAEs to regulatory authorities and the IRB. The protocol will be filed under Investigational New Drug (IND) exemption status with the US FDA.

Safety Measures

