Participants will undergo comprehensive medical evaluation by the study physicians. Medical history, family history, physical and neurological examination (including anthropometric measurements and fundoscopic exams), routine hematology, thyroid function, and blood chemistry (including liver profile), bone X-ray for bone age, and electrocardiography will be performed to determine eligibility for participation. Patients will be monitored for safety and tolerability at weeks 2, 4, 8, and 12 in both treatment phases – see Table 1 and 2. There are a number of tertiary outcomes designed to monitor the safety of rhGH (see Tables 1 and 2) and will be reported to the DSMB (see Stopping Conditions).

Our preliminary phenotyping studies characterizing cognitive and adaptive functioning in Phelan-McDermid syndrome suggest that these children and adults have ID. This sample was significantly delayed in receptive language, expressive language, and overall functional communication skills. We will specifically be recruiting children with iASD who also have ID. As such, it is impossible to directly query these children using verbal methods with respect to safety and tolerability. Instead, we rely on parent report using open-ended methods and a modified SMURF, in addition to physical and neurological exams, and laboratory measures.

Monitoring for AEs will be conducted during scheduled and unscheduled visits per clinical and laboratory assessments. If a subject develops significant neurological signs and symptoms (e.g. cerebrovascular event), they will be seen immediately for a comprehensive evaluation, appropriate treatment, and removal from active participation in the study. We will also apply criteria for attribution of AEs by means of the following descriptors and codes.

- unrelated to treatment 1
- unlikely related to treatment 2
- possibly related to treatment 3
- probably related to treatment 4
- definitely related to treatment 5

Stopping Conditions for Individual Subjects

The following criteria will be used to identify possible adverse treatment events, which will indicate the need to halt active participation of the subject in the rhGH study

- Withdrawal of Consent
- PI or any regulatory authority (Safety Monitoring Board, IRB) believe withdrawal is necessary for the subject's health, well-being, or best interests.
- PI or any regulatory authority believe that withdrawal is necessary for the subject's health, well-being, or best interests

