- Laboratory: any abnormality on any test with adverse event (AE, Common Terminology Criteria for Adverse Events, National Cancer Institute, scales) ≥ 3 or greater at any time in the study
- Any AE of any sort (clinical, laboratory) ≥ 4 will result in halting for the individual and also for the study as a whole.

To avoid bias, all analyses will include all subjects, including those withdrawn from the study, regardless of adherence to study protocol. Especially in an exploratory trial of a novel, unproven treatment, the safety of subjects is our primary *overriding* concern. If there is doubt concerning a subject's safety, the default mode will be withdrawal from treatment or active study participation, followed by close observation (safety follow up visits) and recommendation of standard treatment.

Return of a subject to active study participation will not be permitted, except if a transient clinical or laboratory abnormality unrelated to study treatment has occurred and subsequent permission of the Safety Monitoring Board to return the patient to active study has been provided.

If a subject is withdrawn from active study during screening or observation phases of the study, they will be returned to the referring physician and standard care will be recommended; in addition we will request the subject's participation in an end-of-study visit.

If a subject is withdrawn from active study during rhGH treatment, they will also be returned to the referring physician and standard care will be recommended; however, in this case, we will in addition request the subject's participation in clinical and laboratory safety assessments and follow up per protocol schedule.

Stopping Conditions for Study as a Whole

The study will be halted* if two patients experience stopping conditions. (Exceptions for this criterion: Patients who withdraw voluntarily for reasons not directly related to or intrinsic to the study, e.g. incidental considerations such as concerns about travel time to study visits, unexpected pregnancy in the family, etc. Clearly, patients who experience adverse effects during rhGH treatment would count towards this criterion for whole study stopping).

In addition, the study will be halted if one patient experiences a serious related adverse effect (grade \geq 4 AE).

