All safety data will be reported to the DSMB every six months and to the IRB annually, or, in the case of any major safety concern or question, immediately. If any study stopping condition occurs, this will be reported immediately and the study halted, pending review by the DSMB and IRB, and until the decision by regulatory authorities to resume, suspend or close the study has been made.

*Operationally, "halting" will ordinarily mean that no further screening of new subjects and no treatment initiation will occur until the safety issue has been investigated and resolved (i.e., a final decision has been made to resume, suspend or close the study has been made). Enrolled study participants who have no new symptoms or adverse effects will ordinarily be allowed to continue study observation or treatment without interruption while the safety issue is being investigated, unless it is the contemporaneous judgment of the PI or subsequent judgment of the Safety Monitoring Board or IRB that it is unsafe to do so, in which case all observation or treatment interventions will be suspended forthwith.

Tables

Table 1. Safety and Screening Measures

Measures*	Baseline	Week 4	Week 8	Week 12
Physical and neurological exam	X			X
Fundoscopy	X			X
Electrocardiography	X			X
Bone X-ray for bone age	X			X
Pregnancy Test	X			X
Height	X			X
Weight	X			X
Head circumference	X			X
Side effect monitoring**	X	X	X	X

*Safety measures will be performed at these time points in *both* phases of the crossover trial.

**In addition to the above, side effect monitoring will occur at week 2 by phone, or at any point in person as needed, in both phases.

Table 2. Laboratory Safety Measures

Measures	Baseline*	Week 4*	Week 8*	Week 12*
Electrolytes (Na, K, Cl, CO2)	X			X
Complete blood count	X			X
Liver function panel	X			X
Thyroid function (TSH/T3/T4)	X			X
Renal function (BUN/CR)	X			X
Hemoglobin A1c	X			X
Albumin	X			X
Glucose (fasting)	X			X
Insulin (fasting)	X			X
Lipid profile	X			X
IGF-1 / IGF-BP3	X	X	X	X

*Laboratory safety measures will be performed at these time points in *both* phases of the crossover trial

Table 3. Dose Titration Schedule

Week	Dose
Week 1 and 2	0.15 mg/kg/week divided into daily doses
Week 3 to 12	0.30 mg/kg/week divided into daily doses

Literature Cited

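### Table 2 schedules no glucose or thyroid test between baseline and week 12, so the grade 3 laboratory stop cannot interrupt rhGH on a scheduled result for these harms, although the text promises four-weekly laboratory checks

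*Combined protocol and SAP*

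**What the plan says.** Four places in the combined protocol and SAP bear on this point.

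- **Approach, Aim 3, Outcome measures.** After describing the side-effect interview, the text says that extensive clinical and laboratory "assessments will occur every four weeks during visits (see Protection of Human Subjects". In the extracted text an outcome table splits this sentence, but its sense is clear.
- **Safety Measures.** "Patients will be monitored for safety and tolerability at weeks 2, 4, 8, and 12 in both treatment phases", with the detail referred to Tables 1 and 2.
- **Table 2, Laboratory Safety Measures.** The columns are baseline and weeks 4, 8 and 12, and the footnote reads "Laboratory safety measures will be performed at these time points in" both phases. Electrolytes, blood count, liver panel, thyroid function, renal function, HbA1c, albumin, fasting glucose, fasting insulin and lipids are marked at baseline and week 12. IGF-1/IGF-BP3 is marked in all four columns.
- **Stopping Conditions for Individual Subjects.** A child stops for "any abnormality on any test with adverse event (AE, Common Terminology Criteria for Adverse Events, National Cancer Institute, scales") of grade 3 or higher, whenever in the study it occurs.

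Risks to the Subjects lists insulin resistance and low thyroid hormone among the less common effects of rhGH.

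**The concern.** The narrative and the table give different laboratory schedules, and no sentence says which one prevails. The difference matters because a stopping rule can act only on results that exist. If Table 2 is what staff follow, the tests that would show a glucose or thyroid effect are next due at the end of the phase. By then there is no rhGH left to withhold in that phase.

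The population makes this more important. The protocol says of these children that "it is impossible to directly query these children using verbal methods with respect to safety and tolerability", and that it relies on parent report, examinations and laboratory measures instead. Scheduled tests carry more weight when the patient cannot describe symptoms. The halt of the whole study "if two patients experience stopping conditions" is built on individual stops, so it waits for the same results.

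**Working it through.** **Step 1: count the schedule (Table 2).**

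- Rows: 11.
- Marked at baseline and week 12 only: 10.
- Marked at all four time points: 1 (IGF-1/IGF-BP3).
- Marks per phase as printed: 10 × 2 + 1 × 4 = 24.
- Marks per phase if every test were four-weekly: 11 × 4 = 44.
- Difference: 44 − 24 = 20, which is ten tests at weeks 4 and 8.

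The IGF-1 row fills every column and the other rows leave the two middle cells empty, so the pattern looks deliberate and not like a broken table. The baseline sample is also a scheduled result, but it precedes dosing. The relevant quantity is therefore the first scheduled result on treatment.

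**Step 2: reproduce the plan's course dose (Drug Administration; Table 3).**

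- Average weight: 24.65 kg.
- Weeks 1 and 2: 0.15 × 24.65 = 3.7 mg per week.
- Later weeks: 0.30 × 24.65 = 7.4 mg per week.
- Course: 2 × 3.7 + 10 × 7.4 = 81.4 mg, which is the plan's figure.

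Drug Administration labels the higher dose as weeks 3-10 in one sentence. The 81.4 mg total needs ten weeks at that dose, as Table 3 has it (weeks 3 to 12).

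**Step 3: dose given by each possible test date.**

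| Test at | Dose given | Share of course | Still to give |
|---|---|---|---|
| Week 4 | 2 × 3.7 + 2 × 7.4 = 22.2 mg | 27% | 59.2 mg |
| Week 8 | 2 × 3.7 + 6 × 7.4 = 51.8 mg | 64% | 29.6 mg |
| Week 12 | 81.4 mg | 100% | 0 mg |

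Under Table 2 the glucose and thyroid results fall in the last row. On a four-weekly schedule the first would fall in the top row.

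**Step 4: allow for upward titration.** The dose may be raised on IGF-1 to a maximum of 0.45 mg/kg/week. As an assumed extreme, take that dose from week 5 onward. The course is then 2 × 0.15 + 2 × 0.30 + 8 × 0.45 = 4.5 mg/kg, of which 0.9 mg/kg is given by week 4 (0.9 / 4.5 = 20%). A week 4 test would thus fall after 20% to 27% of the course. Table 2 still puts the first result after 100%.

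**Step 5: what the stopping rule can act on.** With no scheduled glucose or thyroid result strictly between baseline and week 12, the grade 3 rule can end rhGH early for these harms only through an unscheduled test.

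**The case against.** The strongest reply is that the conflict largely resolves itself. The Outcome measures sentence ends by pointing to Protection of Human Subjects, and Safety Measures points to the tables. Both send the reader to Table 2, and the four-weekly IGF-1 draw is, literally, a laboratory assessment every four weeks. This stands as far as it goes: Table 2 is probably the operating schedule. It does not close the gap, because that is the reading under which no glucose or thyroid test falls mid-phase.

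A second reply is that other routes exist. "Monitoring for AEs will be conducted during scheduled and unscheduled visits per clinical and laboratory assessments", and after an adverse event "The investigator may perform or arrange for the conduct of supplemental measurements and/or evaluations". Investigator judgement and the grade 4 rule also remain. These are real safeguards, so it would be wrong to say the children go unmonitored. Tests prompted by an event do, however, need someone to notice the event first.

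A third reply is that the doses are conventional. The protocol gives 0.3 mg/kg/week as an average dose in idiopathic short stature and ties the 0.45 maximum to the package insert. In the open-label rhGH pilot, IGF-1 Z-scores reached 6 SD against a 2 SD target, but the four-weekly IGF-1 test would show that, and the pilot summary reports no glucose or thyroid abnormality. Nothing here shows that harm is likely.

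A reader might also infer more than the documents support:

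- **That different sites would follow different schedules.** The text describes a single centre.
- **That a definite number of extra children would start treatment before a delayed study halt.** This needs an abnormality that is already grade 3 mid-phase, is missed clinically and is the second stop, all while enrolment is open. No probability is given for any of these, and entrants go to both sequences.
- **That late detection unbalances the two sequences and biases the comparison.** No rate is given, and any effect is probably small.
- **That an insulin result would itself trigger the stop.** The documents give no grading for it.

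**Conclusion.** The point holds as an inconsistency in the safety schedule, with moderate confidence. No estimand, model or test is affected. The narrative promises four-weekly laboratory work, while the table that probably governs provides it for 1 test of 11. On that table, the first scheduled on-treatment glucose or thyroid result comes after all 81.4 mg of the average child's course, where a week 4 test would come after 22.2 mg.

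The conclusion rests on three assumptions: that Table 2 is what staff follow, that the Table 3 doses apply to a 24.65 kg child, and that a glucose or thyroid abnormality can reach grade 3 under the cited scale. The documents show no thresholds, so the last relies on the rule's own wording, which covers any test. The number of children affected cannot be estimated from the documents. The change is worth making because it is cheap and gives an existing rule something to act on.

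**What to change.** 1. **Table 2.** Mark glucose (fasting where feasible, otherwise non-fasting) and thyroid function at weeks 4 and 8 in both phases, using the blood already drawn for IGF-1/IGF-BP3. Fasting insulin at those visits is optional.
2. **Outcome measures.** Replace the general sentence with one that matches, for example: *IGF-1/IGF-BP3, glucose and thyroid function are measured every four weeks in each phase; the other eight tests in Table 2 are measured at baseline and week 12.* (11 − 3 = 8; seven if insulin is added.)
3. **Handling.** Send the added results to the safety physician and not to the independent evaluator, who is to stay blind to side effects.

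HbA1c can stay at baseline and week 12, since glucose covers the same harm mid-phase. The stopping rules and the analysis do not change. If the sponsor prefers the sparser schedule, the Outcome measures sentence still needs correcting.

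The cost is about 30 children × 2 visits × 2 phases = 120 extra panels if all complete both phases. No extra needle stick is needed, which fits the protocol's aim of keeping blood sampling to a minimum. The burdens are slightly more blood, possible fasting at two more visits per phase in children who may find it hard, and more chances of an incidental grade 3 result, which could stop a child or count towards a halt.
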